2. Identify putative psychological mechanisms of response to CPT through pre-, mid-, and post-intervention measures of PTSD severity as well as measures of hopelessness, self-blame, and negative self-related thoughts.

Hypotheses:

NIMH Branch:

1. It is predicted that feasibility will be established by obtaining $\geq 80\%$ participant retention for the CPT course. As additional metrics of feasibility we will assess eligibility;

[†]For the NIMH branch, any historical data (i.e., information that is stable and is not expected to change over time) that has already been collected through protocol 2014-1106, we will obtain this data from the PI's database (2014-0350) and will not re-administer these assessments under the current protocol.

- participation; compliance; adherence; competence; and safety.
2. It is predicted that group CPT acceptability will be established by obtaining mean scores ≥ 27 on the CSQ-8.
 3. It is predicted that assessment collection feasibility will be established by obtaining 100% of PCL-5s at each timepoint for participants retained at that timepoint.

WPP Branch:

1. It is predicted that compared to the active control group, the CPT group will exhibit significantly greater reductions in PTSD symptom severity (primary outcome measure) as well as reductions in the severity of depression and general anxiety symptoms (secondary outcome measures) over the course of treatment.
2. It is predicted that the CPT group will exhibit greater reductions in hopelessness, self-blame, and negative self-related thoughts compared to the active control group.
 - a. Within only the CPT group, the reductions in hopelessness, self-blame, and negative self-related thoughts will precede the reduction in PTSD symptoms.
 - b. Within only the CPT group, the reduction in PTSD symptom severity will be mediated by reductions in hopelessness, self-blame, and negative self-related thoughts.

Trainee Project:

This study is part of the dissertation project of [name].

Participants:

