Participants will be eligible to participate if they meet the following criteria: 18 years of age or older; IQ greater than or equal to 70; reading level of 4th grade or higher; no active symptoms of psychosis that would interfere with the individual's ability to participate in the group, no active suicidal ideation with intent or plan, able and willing to participate in group therapy; no scheduled release date before the end of the treatment group; and not currently enrolled in trauma focused treatment that is historical or involves processing of trauma itself. Other vulnerable populations within the prison setting (i.e., pregnant women or individuals appearing to lack the capacity to provide informed consent) will not be eligible for participation. Research suggests that a PCL-5 score between 31-33 indicates a probable diagnosis of PTSD. Accordingly, participants will be eligible to participate if they score a 31 or greater on the PCL-5 within two months of starting the study treatment. We will identify participants meeting these eligibility criteria from the pool of subjects who have previously participated in another IRB-approved protocol led by PI [name] (2014-1106).

WPP Branch:**Taycheedah Correctional Institution:**

Participants will be eligible to participate if they meet the following criteria: 18 years of age or older; no serious self-harm past 6-months (in clinical observation due to self-harm), no disciplinary segregation time in past 6-months, have not participated in the previous CPT groups with UW Project (NIMH branch), no active symptoms of psychosis that would interfere with the individual's ability to participate in the group, no active suicidal ideation with intent or plan, able and willing to participate in group therapy; not currently enrolled in trauma focused treatment that is historical or involves processing of trauma itself; no scheduled release date before the end of the treatment group; and able to understand the consent form as measured by the consent quiz. Research suggests that a PCL-5 score between 31-33 indicates a probable diagnosis of PTSD. Accordingly, participants will be eligible to participate if they score a 31 or greater on the PCL-5 within two months of starting the study treatment. We will identify participants meeting these eligibility criteria from the DOC list of residents on the waitlist for trauma treatment.

Kettle Moraine Correctional Institution:

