Participants will be randomly assigned to the CPT or the active control groups (randomization process specified in “Randomization and Blinding”). The CPT group will engage in 12, 90-minute treatment sessions (18 hours total). With the optional opportunity to take 15-20 minutes after each session to de-stress and calm down if necessary. These sessions will take place over 6 to 12 weeks, depending on session frequency. CPT group-members are also asked to complete weekly homework (approximately 12 hours total). A maximum of 8 participants, but no less than 3 will be included in each CPT group. When the waitlist control group reaches the treatment phase, if the participant count fall below 3, additional participants will be enrolled to maintain sufficient numbers. Data collection during treatment will mirror that of the active waitlist control group. Participants will be notified via institutional mail which group they have been enrolled in.

In addition to the treatment groups, CPT and control group members will complete a PCL-5 at the beginning of each session. As well as, pre-treatment testing session two weeks prior to the start of treatment. After treatment session 5, CPT and control group members will complete mid-treatment testing assessments. Participants will be called down individually to complete these assessments in a private room with a research assistant after completing the 5th therapy session, but before completing the 8th therapy session. CPT and control group members will then complete post-treatment testing within one week after completing week 6 of treatment. One month after the treatment is completed, CPT and control group members will complete follow-up testing and interviewing about their experience in the treatment groups and will have one follow up CPT session 6-8 weeks post-treatment. Post-treatment and one-month follow up- testing will follow the same procedure as pre-treatment and mid-treatment testing. Final follow-up will occur three months after the end of treatment. Procedures will be the same as other timepoint follow-ups. CPT and control group members will be asked to complete 18 sessions in total (pre-treatment, mid-treatment, post- treatment, one-month follow up-testing, three-month follow-up treatment, 12 group sessions and one follow-up CPT session).

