Analysis of effectiveness: Treatment efficacy will be determined by the change (from pre-intervention to post-intervention timepoints) for the primary outcome (PTSD) and secondary outcomes (e.g., depression) for each group. Repeated measures ANOVAs will be conducted for each group. One-way ANOVA will be used to test for group differences in score changes from pre-intervention to post-intervention, with follow-up pairwise tests (if warranted), using Tukey's post-hoc tests. IQ and age will be included as covariates in all analyses.

Exploratory analysis of moderators: As an exploratory follow-up analysis, we will examine potential moderators of effectiveness (details of measures in "Baseline Assessments" above). Following published guidelines for randomized controlled trials [45,46], moderators of treatment outcome will be tested in regression models, in which the post-intervention primary outcome measure (PCL-5 score) is regressed simultaneously onto 1) dummy-coded group assignment (CPT vs control), 2) the hypothesized moderator, 3) the group x hypothesized moderator interaction, 4) the pre-intervention primary outcome measure (PCL-5 score), and 5) any covariates of non-interest. The regression coefficients of interest are the main effect of the moderator and its interaction with group. A main effect independent of an interaction indicates the moderator predicts symptom reduction regardless of group assignment. An interaction with group indicates that the moderator predicts symptom reduction more strongly in one of the treatment conditions (i.e., specificity of moderation).

Adherence by the therapists will be measured by ratings of the presence or absence of five session elements (scores 0-5) by the clinical supervisors, as in previous CPT studies [16,18]. Adherence ratings will be collected for two audiotaped group sessions out of each 12-session intervention (16.7% of sessions). Our study goal is adherence scores ≥ 4 for each session.

Competence of the therapists will be measured by ratings of the quality of session elements (scores 1-7; 1="not satisfactory", 4="satisfactory", 7="excellent") by the clinical supervisors, as in previous CPT studies [16,18]. Competence ratings will be collected for two audiotaped group sessions out of each 12-session intervention (16.7% of sessions). Our study goal is competence scores ≥ 4 for each session.

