NIMH: Potential eligible participants will be identified through a research database maintained by the P.I. (2014-0350). This database includes demographic (e.g. age, race, IQ) and psychological variables (e.g., psychopathy score, substance abuse) collected during our initial screening and interviewing protocol. Participants who previously scored highly on a self-report measure of PTSD symptomology (PTSD Checklist for DSM-5 > 33 [33]) that is included in our initial screening process will be prioritized for this study. All prison studies that we conduct utilize this database to recruit eligible participants.

WPP: Potential eligible participants will be identified through the trauma treatment waitlist at the facilities. These participants have been screened for active psychosis, suicidality, and self-harm or will be identified through a research database maintained by the P.I. (2014-0350). This database includes demographic (e.g. age, race, IQ) and psychological variables (e.g., psychopathy score, substance abuse) collected during our initial screening and interviewing protocol. Participants who previously scored highly on a self-report measure of PTSD symptomology (PTSD Checklist for DSM-5 > 33^[33]) that is included in our initial screening process will be prioritized for this study. All prison studies that we conduct utilize this database to recruit eligible participants.

Study Stopping:

Participants can withdraw themselves from this study at any time. Participants may be withdrawn from the study treatment group under the following circumstances; if they endorse suicidal ideations with intent or plan and/or it significantly increases throughout the course of treatment (explained below under “Suicidality Risk”), PTSD symptoms significantly worsen over time due to treatment per participants report and clinicians’ discretion (explained below under “PTSD Symptoms Worsening”), noncompliance with treatment requirements or consistently being harmful or disruptive to other group members or the therapist, or serious adverse events directly related to treatment. In the event that one of these circumstances occurs and the participant is not withdrawn from the study based on clinician discretion, the clinician will document this circumstance and rationale. A serious adverse event is classified as life threatening, requires inpatient hospitalization, persistent or significant disability or incapacity, or is an important medical event [51].

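### The WPP effectiveness analysis does not say whether the per-arm ANOVAs or the between-group test decides efficacy, and the between-group test leaves out baseline PCL-5

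*Combined protocol and SAP*

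**What the plan says.** The key text is in Measurement of Specific Aims, WPP Branch, Specific Aim #1, Analysis of effectiveness. It makes three statements in this order:

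- The criterion: "Treatment efficacy will be determined by the change (from pre-intervention to post-intervention timepoints) for the primary outcome (PTSD") and for the secondary outcomes, with the change taken in each group.
- A test inside each arm: "Repeated measures ANOVAs will be conducted for each group".
- A test between arms: "One-way ANOVA will be used to test for group differences in score changes from pre-intervention to post-intervention".

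It then adds that "IQ and age will be included as covariates in all analyses". Baseline PCL-5 is not listed.

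Elsewhere:

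- Hypotheses, WPP Branch, item 1 is a between-group statement: "compared to the active control group, the CPT group will exhibit significantly greater reductions in PTSD symptom severity".
- Eligibility Criteria select on the primary outcome scale: "participants will be eligible to participate if they score a 31 or greater on the PCL-5 within two months of starting the study treatment".
- Participant Recruitment gives priority to "Participants who previously scored highly on a self-report measure of PTSD symptomology" for WPP candidates found through the research database.
- Research Design and Procedures has a PCL-5 completed at intake to establish probable diagnosis. Its WPP part also describes a "pre-treatment testing session two weeks prior to the start of treatment", and the Questionnaires section puts the PCL-5 in the pre-treatment battery.
- Randomization and Blinding stratifies WPP allocation on PCL-5 total score.
- The exploratory moderator model regresses post-intervention PCL-5 on group with pre-intervention PCL-5 in the model.

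**The concern.** The sentence that says how efficacy is decided refers to change in each group, and the first test named is a within-arm test. A within-arm test cannot separate CPT from the passage of time, repeated assessment, other care, or regression to the mean among people who entered because the same scale was high. A significant fall under CPT beside a non-significant fall under control is also not evidence that the arms differ. The hypothesis is about the difference between arms, and the test that addresses it is listed second, with no statement that it is the one that counts. A report could therefore cite the criterion sentence for a within-arm claim even if the randomised contrast were null.

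There is a second, smaller point. The between-group test uses change scores and omits the strongest predictor available, baseline PCL-5, although the trial collects it, stratifies on it and adjusts for it in the moderator model.

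**Working it through.** **The plan's own figure.** There is none for PCL-5. The only power calculation (Statistical Considerations, n = 32) concerns retention, 60% against 80%, one-sided 5%, power 80%. It reproduces (32.6 by the normal approximation, 31.6 by the arcsine method) but has no bearing on this analysis.

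**Inputs.** From the documents: entry cut-off PCL-5 ≥ 31; 60 per arm in Statistical Considerations, or about 40 per arm if the WPP total of 80 is split equally (that statement's male and female counts add to 100). Assumed, because the documents give none: SD 16, retest correlation r 0.75 to 0.85, screened-pool mean μ of 25 to 45, normal scores, no treatment effect.

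**Step 1: eligibility score used as the pre score.** Let a = (31 − μ)/SD and λ = φ(a)/[1 − Φ(a)]. The expected fall is (1 − r) × SD × λ.

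| μ | a | λ | Fall, r = 0.75 | Fall, r = 0.85 |
|---|---|---|---|---|
| 25 | 0.375 | 1.051 | 4.2 | 2.5 |
| 35 | −0.25 | 0.646 | 2.6 | 1.6 |
| 45 | −0.875 | 0.336 | 1.3 | 0.8 |

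The variance of change is (1 − r)² × SD² × (1 + aλ − λ²) + SD² × (1 − r²). For μ = 25, r = 0.75 this is 0.0625 × 74.1 + 256 × 0.4375 = 116.6, so the SD of change is 10.8. At n = 40 the standardised fall is 4.2/(10.8/√40) = 2.46, and the chance of a significant within-arm fall is 67%. Over the whole grid the chance is 8% to 67% at n = 40 and 11% to 84% at n = 60, against 2.5% nominal in that direction.

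**Step 2: separate pre-treatment PCL-5.** The expected fall becomes (r between screen and pre − r between screen and post) × SD × λ.

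- Equal correlations: the difference is 0, the fall is 0, and the chance stays at 2.5%.
- Correlations that decay with time, μ = 35. Screen-pre/screen-post 0.80/0.70 or 0.85/0.75: 0.10 × 16 × 0.646 = 1.0 point. 0.85/0.80: 0.05 × 16 × 0.646 = 0.5 point. With pre-post correlations of 0.75 to 0.85, the chance of a significant within-arm fall is 6% to 9% at n = 40 and 7% to 12% at n = 60.
- μ = 25, worst of these cases: 0.10 × 16 × 1.051 = 1.7 points, and a chance of 25% at n = 60.

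**Step 3: the planned between-group test.** Randomisation gives both arms the same expected fall, so it cancels. Simulation with no treatment effect and the screening score as baseline (wider ranges: SD 15 to 18, r 0.6 to 0.9, μ 25 to 45) gave type I error of 4.3% to 5.9% for the comparison of change scores. In the same runs the pattern of a significant fall under CPT but not under control occurred in about 2% to 26% of trials at 40 to 60 per arm.

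**Step 4: baseline adjustment.** With equal pre and post SDs σ, the variance of change is 2σ²(1 − r) and the ANCOVA residual variance is σ²(1 − r²). The ratio is (1 + r)/2: 0.875 at r = 0.75 (about 12% lower) and 0.925 at r = 0.85 (7.5% lower). With unequal SDs the difference is (σ_pre − rσ_post)², which is never negative, so ANCOVA loses nothing beyond one degree of freedom.

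**The case against.** The strongest reply is that the plan already contains the right test. The between-group ANOVA follows directly after the per-arm ANOVAs, Hypothesis 1 is between-group, and allocation is randomised and stratified on PCL-5. The paragraph can be read as: compute change in each group, then compare the groups. Nothing says that a within-arm fall is sufficient, or that significance in one arm only counts as efficacy. All of this stands.

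A reader might go further and infer that efficacy will be judged by the within-arm tests alone, so that regression to the mean will pass for a treatment effect. The documents do not support that, because they plan the between-group test and state the hypothesis in those terms. A reader might also take the 8% to 84% range as the trial's false-positive rate. It is not. It is the chance of a within-arm p below 0.05, and it needs the eligibility score to serve as the pre score. The intake PCL-5, the later pre-treatment session and the pre-treatment battery point towards a separate measurement, though the text does not say so outright. The upper end also needs a pool mean below the cut-off, which is unlikely for people drawn from a trauma-treatment waitlist.

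Two further replies hold. Priority for earlier high scorers adds little, since an earlier score has largely regressed by a later baseline. Other care is unquantified: concurrent trauma-processing treatment is excluded, and the plan states that it knows of no evidence that other prison group programmes affect PTSD symptoms. Finally, a randomised change-score comparison is valid without baseline adjustment, so that part of the point concerns precision, not bias.

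What remains is that the plan does not name the deciding test, and its criterion sentence points to the per-group change.

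**Conclusion.** The point holds as a gap in the decision rule and a missed gain in precision; the primary comparison is not invalid. The between-group test keeps type I error near 5% as far as regression to the mean is concerned. The per-arm tests cannot carry an efficacy claim, whatever the size of the regression.

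That size is conditional on SD 16, r 0.75 to 0.85 and a pool mean of 25 to 45, none of which is in the documents. If the eligibility score is the pre score, the expected fall without treatment effect is 0.8 to 4.2 points in each arm. If the pre-treatment PCL-5 is separate, as the text suggests, it is about 0 to 1 point at a pool mean of 35, and the inflation of the within-arm test may be small or nil. The precision gain is about 12% in variance at r = 0.75, assuming equal pre and post SDs. This is a free or cheap improvement.

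**What to change.** In Analysis of effectiveness:

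- State that efficacy is determined solely by the randomised between-group contrast: post-intervention PCL-5 by group, with baseline PCL-5 as a covariate (ANCOVA).
- Do the same for BDI-II and BAI, each with its own baseline.
- Replace the per-arm repeated-measures ANOVAs with mean changes and confidence intervals, labelled descriptive and not as efficacy tests.
- State which PCL-5 is the baseline: the eligibility score or the pre-treatment session score.

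The cost is analysis wording. No new data are needed, since the baseline scales are already in the battery. The sponsor gives up within-arm significance claims.

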Participants will be adult male and female individuals incarcerated in Wisconsin state prisons. Males will be recruited from Oakhill Correctional Institution (OCI), a minimum-security Wisconsin DOC facility housing over 600 adult males and Fox Lake Correctional Institution (FLCI), a medium-security Wisconsin DOC facility housing over 1,300 adult males. Females will be recruited from Taycheedah Correctional Institution (TCI), a mixed-security Wisconsin DOC facility housing over 800 adult females.

Participants will be withdrawn from the study if they exhibit disruptive behavior (e.g., verbal or physical abuse towards another participant or therapist, repeatedly do not respect group rules outlined at the beginning of treatment) any time throughout participation. Prior to beginning any study procedures, informed consent will be obtained orally and in writing. During the informed consent process, eligible participants will be provided with detailed information about the study, including their right to refuse or discontinue participation at any time and the fact that their decision to participate or decline will have no bearing on their standing within the criminal justice system.

[†] For the NIMH branch, any historical data (i.e., information that is stable and is not expected to change over time) that has already been collected through protocol 2014-1106, we will obtain this data from the PI's database (2014-0350) and will not re-administer these assessments under the current protocol.

Eligibility Criteria:**Inclusion Criteria:****NIMH Branch:**

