To ensure that our randomization process results in treatment groups that are balanced on key variables that might affect treatment response, participants will be assigned to groups through stratified randomization, in which randomization occurs within specific strata of different potential moderating variables and assures equal assignment to each group across these variables. Participants will be stratified/randomized based on PTSD severity (PCL-5 total score).. The stratified randomization will use group code numbers (1 & 2) rather than the intervention title, thus eliminating any chance of systematically biasing the group assignment.

While it is impossible for the therapists and participants to be blind to the group assignment, the research members performing the pre-treatment, mid-treatment, post-treatment, one-month and three-month follow-up assessments will be blind to the group assignment. The study therapist will not conduct assessments once participants have assigned to their respective treatments (e.g., pre-, mid-, post-, or follow-up assessments). Additionally, one graduate research assistant will schedule

participants according to the randomization, thus minimizing the possibility of systematically biasing the outcome and mediator assessments.

Treatment:

NIMH & WPP Branches:

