Each CPT group will enroll 6-8 members and will meet weekly or biweekly for 12 group sessions including one follow up CPT session. Participants will be referred to by their preferred first names. The CPT protocol will follow the published manual [15]. Session 1 begins with orientation to group treatment and group rules, education about PTSD, an overview of treatment, and an assignment to write an impact statement about the personal meaning and effect of the traumatic event. After reading and discussing the meaning of the traumatic event in Session 2, group members are introduced to the identification of and relationship among events, thoughts, and emotions. At the end of Session 3, group members are given the assignment of recording events, thoughts, and emotions throughout the week to establish the relationships between thoughts and emotions within their own lives. During Session 4, cognitive therapy begins with Socratic questions regarding self-blame and other distortions regarding the event. In Sessions 5-6, the focus of the therapy shifts to teaching clients to challenge and change their beliefs about the meaning of the event and the implications of the trauma for their lives. Group members are first taught to challenge a single thought by asking themselves a series of questions. They are then taught to identify problematic patterns of cognitions that have come to represent a style of responding. From that point, beginning with Session 7, group members use worksheets that incorporate the earlier activities as well as the development of alternative, more balanced self-statements. In Sessions 7-12, group members are asked to focus on one of the five core themes of CPT each week (safety, trust, power/control, esteem, or intimacy) and correct any overgeneralized beliefs related to that theme. In Session 11, group members are asked to rewrite their impact statements to reflect their current beliefs, and these revised statements are then used in Session 12 to evaluate gains made in treatment and areas in which they wish to continue working. Following the completion of the 12 CPT sessions, an additional follow-up group CPT therapy session will be provided. This follow-up CPT session is recommended by the CPT manual and typically occurs 2-3 months after the end of the 12-session treatment group. The group follow-up CPT session is designed to check-in with participants to see how they are doing, work through any problems/difficulties they have had, and to reinforce the strategies and skills they learned from the treatment group. At the start of each treatment session, the participants will be asked to complete the PCL-5. At the end of treatment sessions, participants will be given the option to de-stress for 15-20 minutes.

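### The WPP between-arm ANOVA on PCL-5 change leaves out the stratifying baseline, facility and therapy group. The effects partly offset, so its type I error may be near 5% but is not controlled.

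*Combined protocol and SAP*

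**What the plan says.** In the combined protocol and SAP, Measurement of Specific Aims (WPP Branch, Analysis of effectiveness) sets the between-arm test: "One-way ANOVA will be used to test for group differences in score changes from pre-intervention to post-intervention". It adds that "IQ and age will be included as covariates in all analyses". No other adjustment is named. The design has three features that this model does not carry.

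- **Baseline PCL-5.** Randomization and Blinding (WPP Branch) states: "Participants will be stratified/randomized based on PTSD severity (PCL-5 total score". The exploratory moderator regressions do adjust for "the pre-intervention primary outcome measure (PCL-5 score"; the main test does not.
- **Facility.** WPP runs in a women's prison and in one or more men's prisons: "Females will be recruited from Taycheedah Correctional Institution (TCI), a mixed-security Wisconsin DOC facility". The list of men's sites varies. The WPP eligibility section has an entry for "Kettle Moraine Correctional Institution", the WPP design paragraph pairs TCI with FLCI or OCI, and Multiple Sites lists only OCI, FLCI and TCI.
- **Therapy group.** Under Treatment, "Each CPT group will enroll 6-8 members"; under Research Design and Procedures, "A maximum of 8 participants, but no less than 3 will be included in each CPT group". Under Therapists, WPP groups are led by each facility's own psychological services staff.

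The documents also differ on whether control participants meet before the post-treatment comparison. The enrolment paragraphs under Participants and the WPP design paragraph describe a waitlist. The WPP hypotheses, Research Design and Procedures, Qualitative Data Collection and the WPP part of Treatment describe an active control with sessions, although the last of these also uses the word waitlist.

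**The concern.** The WPP objective is to determine effectiveness, and this is the only stated between-arm test of its primary outcome. An analysis should reflect how participants were allocated and how treatment was delivered. Here the omissions pull in opposite directions. A baseline that was balanced by stratification but left in the error term makes the standard error too wide. Correlated outcomes within therapy groups make it too narrow. The net error rate then depends on quantities that the documents do not give. The obvious repair, adding baseline and site, removes the conservative part and leaves the clustering uncorrected.

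**Working it through.** **The plan's own figure.** Statistical Considerations gives one calculation, n = 32 for retention of 60% against 80%, one-sided 5%, 80% power. It reproduces: [1.645√(0.6×0.4) + 0.842√(0.8×0.2)]² / 0.2² = 32.6, and the arcsine form gives 31.6. It concerns retention and says nothing about the ANOVA. No error rate, effect size, ICC or correlation is stated for the WPP test, so the values below are assumptions.

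**Closed form.** Set the SD of pre and post scores to 1, with correlation r.

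- Variance that the planned test uses: 2(1−r), which splits into (1−r)² from baseline and (1−r²) from the residual.
- True variance: (1−r)²×0.363 + (1−r²)×D. Here 0.363 = 1−2/π is the baseline variance left after a balanced median split. D is 1+6×ICC with groups of 7 in both arms, or 1+3×ICC averaged over arms if only CPT is clustered.
- Type I error: 2[1−Φ(1.96√(used/true))].

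For r = 0.5 the variance used is 1.0.

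- ICC 0: true 0.25×0.363+0.75 = 0.841; critical value 2.137; error 3.3%.
- ICC 0.05: CPT only, true 0.953, error 4.5%; both arms, true 1.066, error 5.8%.
- ICC 0.10: CPT only, true 1.066, error 5.8%; both arms, true 1.291, error 8.5%.

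For r = 0.7 and ICC 0.10 the variance used is 0.6. CPT only: true 0.696, error 6.9%. Both arms: true 0.849, error 9.9%.

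**Facility.** A shift f between two equal facilities adds f²/4 to the variance used. At f = 0.5, r = 0.5 and ICC 0:

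- Arms balanced within facility: nothing is added to the true variance. 1.0625/0.841 gives 2.8%, against 3.3% with no shift.
- Allocation pooled across facilities: both sides gain 0.0625. 1.0625/0.903 gives 3.4%, so facility adds no conservatism.

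**Baseline and facility added, no group term.** The ratio becomes 1/D. At ICC 0.05 the error is 6.8% (CPT only) or 8.6% (both). At ICC 0.10 it is 8.6% or 12.1%.

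**Simulation.** 10,000 null runs per cell; n = 80; two facilities; 20 per arm in each; groups of 6-7; r 0.4 or 0.7; 2 or 4 strata; facility shift 0-0.5 SD; arms balanced within facility. Type I error, %:

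| ICC | Planned, CPT only | Planned, both arms | Baseline + facility, CPT only | Baseline + facility, both arms |
|---|---|---|---|---|
| 0.02 | 2.5-4.6 | 2.6-4.7 | 5.4-6.0 | 5.8-6.5 |
| 0.05 | 3.1-5.4 | 4.1-6.5 | 6.3-7.2 | 7.7-9.0 |
| 0.10 | 3.9-7.1 | 6.1-9.5 | 8.0-8.8 | 11.4-12.3 |

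At ICC 0 the planned test gives 1.8-4.2%. A second simulation reached 11.2% for the planned test at ICC 0.10 with 60 per arm, both arms clustered and r 0.7. With all three terms and Satterthwaite degrees of freedom, the error is 2.8-4.1% at ICC 0-0.02 and 4.0-5.0% at 0.05-0.10. The degrees of freedom matter: with a normal reference, the three-term model still reached 8.0% at ICC 0.10 with both arms clustered.

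**The case against.** The strongest reply is that little harm is shown. With only CPT clustered and ICC up to 0.05, the planned test stays at 1.8-5.4%. The replacement is itself below nominal near ICC 0. The plan calls this aim a preliminary look at efficacy. All of that is correct, and it keeps the point moderate. It does not remove it, because the plan neither fixes which arms are clustered nor limits the ICC.

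Four stronger readings are tempting, and the documents do not support them.

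- *The planned test is biased or clearly inflated.* Under randomisation these omissions affect the standard error, not the expected treatment difference, and in many plausible cases the error rate is at or below 5%.
- *Leaving out facility makes the test conservative.* That needs balance within facility. The plan names PCL-5 alone as the stratifier.
- *Only CPT is clustered, because the control is a waitlist.* Several sections describe control sessions, so this is open.
- *The three terms guarantee control.* Facility staff lead the WPP groups, so one therapist may lead several. Adding one CPT therapist effect per facility, at an assumed 5% of residual variance, put the three-term model at 7.5-9.3% (CPT clustered) or 5.7-7.7% (both) for ICC 0-0.10.

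It is also fair that the simulations use complete data, while the protocol expects attrition and removals from groups.

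**Conclusion.** The concern holds in a limited form. The test omits the stratifying baseline and the therapy-group structure, and it omits facility in a trial run in separate prisons. Its type I error is about 2-7% if only CPT is clustered and up to about 9-11% if both arms meet in groups. This assumes about 80 randomised (60 per arm for the highest figure), r 0.4-0.7, ICC 0-0.10 and a two-sided 5% level. The lowest values also assume arms balanced within facility. At ICC 0.20 the second simulation gave 7.1-9.6% (CPT only) and 12.5-18.2% (both). The number randomised is itself unclear: the WPP paragraph gives 80 but lists 40 men and 60 women (100), and Statistical Considerations gives 60 per arm. At r 0.5, ICC 0.02-0.10 and a 0.3 SD facility shift, variants with n = 100, n = 120, groups of 4, or baseline truncated at 31 left the planned test at 3.6-5.6% or 3.8-8.7%. Confidence is medium: the omissions are plain in the text, but their size rests on assumed values.

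**What to change.** Replace the ANOVA with one mixed model for post-treatment PCL-5. Fixed effects are arm, baseline PCL-5, facility, IQ and age; therapy group is a random effect. Fit by REML with a small-sample correction such as Satterthwaite. Add the three new terms together. Use the same form for BDI-II and BAI, each with its own baseline.

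Before writing the model:

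- Reconcile the sections on whether controls meet in groups before the post-treatment comparison. Put the group effect in both arms if they do, and in CPT only if they do not.
- Reconcile the WPP facility list.
- State whether allocation is balanced within facility, and state alpha.
- Report shared therapist effects as a limitation.

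The cost is SAP wording and a short calibration run on the actual group and facility counts. No new data are needed for the added terms. The statistical price, for ICC 0-0.10, is an interval 0.90-1.14 times the planned width (CPT only) or 0.94-1.29 times (both). For an assumed 0.6 SD effect (r 0.5, facility shift 0.3 SD), power under the planned and the new model is 76% and 80% at ICC 0 and 73% and 69% at ICC 0.10 with CPT only. With both arms clustered it is 75% and 76%, then 72% and 59%. Part of that last gap is the planned test's inflated error. The new model is mildly conservative when the ICC is near zero.
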